4. SCHEDULE OF ASSESSMENTS

Table 4. Schedule of Assessments for Subjects from Core Studies ZX008-1501 and ZX008-1502, and de Novo Subjects**

Study Assessments	OLE Treatment Period				Post-Dosing Visit 17	Cardiac Follow-up Visit 18, 19	
	Visit 1 ^a	Visit 2 ^c		Visits 3-15 (Months 1, 2, 3, 6, 9, 12, 15, 18, 21, 24, 27, 30, and 33)			Visit 16 ^d (EOS/ET) Month 36
Study Day	-28 to 1 ^a	15		30, 60, 90, 180, 270, 365, 455, 545, 635, 725, 815, 905, 995	1085	1099	3 and 6 months post last dose
		Clinic	Phone				
Informed Consent	X						
Entry Criteria	X						
Demographics	X						
Medical/Neurological History	X ^a						
Epilepsy History	X ^{a,b}						
Physical Examination, complete	X ^a				X		X ^e
Physical Examination, abbreviated		X		X			X ^e
Neurological Examination, complete	X ^f				X		
Neurological Examination, abbreviated		X		X			
Vital signs	X	X		X	X		
Weight, Height, BMI	X ^a	X		X	X		
12-lead ECG	X ^a			X	X		X ^e
Doppler ECHO	X ^a			X ^{g,h}	X		X ^e
Urine Pregnancy Test ^h	X			X	X		
Clinical laboratory evaluation (hematology/clinical chemistry/urinalysis, etc)	X ⁱ	X ⁱ		X	X		
Urine THC Panel/Whole blood CBD	X ^a			X	X		
Plasma sample for background AEDs		X		X	X		
Tanner Staging (for subjects >7 to ≤ 18 years)	X ^a			X ^k	X		X ^k
C-SSRS	X ^a			X	X		
CGI-I (assessed by parent/caregiver)	X ^a			X	X		
CGI-I (assessed by principal investigator)	X ^a			X	X		
QOLCE	X ^a			X	X		
EQ-5D-5L (QoL of parent/caregiver)	X ^a			X	X		
HADS (Affect of parent/caregiver)	X ^a			X	X		
BRIEF	X ^a			X	X		

continued

Table 4. Schedule of Assessments for Subjects from Core Studies ZX008-1501 and ZX008-1502, and de Novo Subjects (continued)**

Study Assessments	OLE Treatment Period				Post-Dosing	Cardiac Follow-up	
	Visit 1 ^a	Visit 2 ^c		Visits 3-15 (Months 1, 2, 3, 6, 9, 12, 15, 18, 21, 24, 27, 30, and 33)	Visit 16 ^c (EOS/ET) Month 36	Visit 17	Visit 18, 19
Study Day	-28 to 1 ^a	15		30, 60, 90, 180, 270, 365, 455, 545, 635, 725, 815, 905, 995	1085	1099	3 and 6 months post last dose
PedsQL ⁿ	X ^a			X	X		
Study medication palatability assessment				X ^l			
Subject Diary	D	C/R/D	R	C/R/D	C/R	C/R	
Study Medication	D ^b	C/R/D	R	C/R/D	C/R/D	C/R	
Daily Diary Completion		-----X-----					
Concomitant Medication	X ^a	-----X-----					
Adverse Events	X ^a	-----X-----					
Adverse events of special interest	X ^a	-----X-----					X ^m

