Note: In subjects with more than one occurrence of the same event, the time to onset and duration is based on the earliest occurring event.

Note: Onset day is measured from the first date of ZX008 treatment to onset. Duration for the TEAEs in the placebo group start after the subject starts ZX008 treatment in the OLE.

[1] For subjects treated with Placebo in the core study, TEAEs are counted only after the subject started ZX008 treatment.

Programming note: Use the shell for Table 14.3.1.10.2.1.

Table 14.3.1.10.2.1

Treatment-Emergent Adverse Events that Occurred in at least 5% of Subjects during Double-blind through Open-label Treatment Periods by MedDRA System Organ Class and Preferred Term, Mean Average Dose in ZX008-1503 with Mean Time to Onset (days) and Mean Duration (days)
 Safety Population (Japan)

Programming Notes: Use the Listing 16.2.7.1 shell for the following tables.

Table 14.3.2.1
Listing of Deaths

Table 14.3.2.1.1
Listing of Deaths (Japan)

Table 14.3.2.2
Listing of SAEs

Table 14.3.2.2.1
Listing of SAEs (Japan)

Table 14.3.2.3
Listing of Discontinuations Due to AE

Table 14.3.2.3.1
Listing of Discontinuations Due to AE (Japan)

Laboratory Data

Please see below (also in SAP) for time windows

Time Intervals for Analysis Visits for Laboratory Data and Vital Signs

Analysis Phase/Period	Scheduled Visit Number in ZX008-1503	Analysis Visit Number*	Time Interval (label on output)	Time Interval (Day)	Target Time Point (Day)
Pre-OLE	1	1	Baseline (OLE)	1	1
OLE	2	2	Week 2 (OLE)	2 to 20	15
OLE	3	3	Month 1 (OLE)	21 to 44	30
OLE	4	4	Month 2 (OLE)	45 to 74	60
OLE	5	5	Month 3 (OLE)	75 to 134	90
OLE	6	6	Month 6 (OLE)	135 to 224	180
OLE	7	7	Month 9 (OLE)	225 to 314	270
OLE	8	8	Month 12 (OLE)	315 to 409	365
OLE	9	9	Month 15 (OLE)	410 to 499	455
OLE	10	10	Month 18 (OLE)	500 to 589	545
OLE	11	11	Month 21 (OLE)	590 to 679	635
OLE	12	12	Month 24 (OLE)	680 to 774	730
OLE	13	13	Month 27 (OLE)	775 to 864	820
OLE	14	14	Month 30 (OLE)	865 to 954	910
OLE	15	15	Month 33 (OLE)	955 to 1044	1000
OLE	16	16	Month 36 (OLE)	1045 to 1109	1095
OLE	OLE last Visit**	99	Last Value	Day 2 to Visit 17 date	

Programming Notes:

*For multiple measurements within a time window, please use the closest to the target time point. Note that measurements occurring on the end date of a phase/period or start date of a new phase/period are assigned to the preceding phase/period. For example, measurements taken on OLE Study Day1 are assigned as Baseline (OLE).

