Laboratory parameters – Tests of growth, precocious puberty and thyroid function
Safety Population

Table 14.3.4.5.1
Laboratory parameters – Tests of growth, precocious puberty and thyroid function
Safety Population (Japan)

*For interims and 120-day, please use only last column
For IDMC uses all columns*

Programming Note: Use shell for Table 14.3.4.1 Include correct units in the titles for the **Vital sign parameter**

Table 14.4.1.1
Vital Signs
Safety Population

Table 14.4.1.1.1
Vital Signs
Safety Population (Japan)

Programming Note:

Use shell for Figure 1b in ISS for the the following figures.

Figure 14.4.1.2

Scatterplot of Age (X-axis) and Height (Y-axis) at End of Study during the Open-label Treatment Period
Safety Population

Figure 14.4.1.2.1

Scatterplot of Age (X-axis) and Height (Y-axis) at End of Study during the Open-label Treatment Period
Safety Population (Japan)

Y-axis: ADVS.AVAL where PARAMCD=HEIGHT and AVISIT=EOS/ET and SAFFL='Y'

X-axis: ADSL.AGEEOS

Table 14.4.1.3
 Weight during the Open-Label Study Period over Time by Age Group (2 - <4; 4 - <6; 6 to <12; and ≥12); Summary Statistics
 Safety Population

Age Group: 2-<4 years/ 4 -<6 years/ 6 - <12 years/>=12 years

Visit [1]	Gp1 (N = XX)	Gp2 (N = XX)	Gp3 (N = XX)	Gp4 (N = XX)	Gp5 (N = XX)	Gp9 (N = XX)
Baseline (OLE)						
N	XX	XX	XX	XX	XX	XX
Mean	XX.X	XX.X	XX.X	XX.X	XX.X	XX.X
SD	XX.XX	XX.XX	XX.XX	XX.XX	XX.XX	XX.XX
Median	XX.X	XX.X	XX.X	XX.X	XX.X	XX.X
Min	XX	XX	XX	XX	XX	XX
Max	XX	XX	XX	XX	XX	XX
Week 2 (OLE)						
Observed						
N	XX	XX	XX	XX	XX	XX
Mean	XX.X	XX.X	XX.X	XX.X	XX.X	XX.X
SD	XX.XX	XX.XX	XX.XX	XX.XX	XX.XX	XX.XX
Median	XX.X	XX.X	XX.X	XX.X	XX.X	XX.X
Min	XX	XX	XX	XX	XX	XX
Max	XX	XX	XX	XX	XX	XX
CFB						
N	XX	XX	XX	XX	XX	XX
Mean	XX.X	XX.X	XX.X	XX.X	XX.X	XX.X
SD	XX.XX	XX.XX	XX.XX	XX.XX	XX.XX	XX.XX
Median	XX.X	XX.X	XX.X	XX.X	XX.X	XX.X
Min	XX	XX	XX	XX	XX	XX
Max	XX	XX	XX	XX	XX	XX
...						

TLF Shells

Zogenix International Limited
ZX008-1503

Repeat for all time points						

Note: If a test is repeated at any given visit, the last non-missing result is used in the summary.

Note: this table excludes the De Novo Subjects.

Programming note: Use the Table 14.4.1.3 shell for

Table 14.4.1.3.1

Weight during the Open-Label Study Period over Time by Age Group (2 - <4; 4 - <6; 6 to <12; and ≥12): Summary Statistics
Safety Population (Japan)

Table 14.4.1.4
Weight Over Time during the Open-Label Study Period for De Novo Subjects: Summary Statistics
Safety Population – De Novo Subjects

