Note: Time windows are specified in the statistical analysis plan. In the event of 2 or more assessments in the interval, the assessment completed closest to the target time point are assessed. For the last assessment, the last non-missing value observed.

[1] Percentages are based on the number of subjects with a baseline weight and a weight at the visit meeting the criteria noted in the row.

[2] A subject recovered, if they had a weight recorded after the visit being summarized that was within 1% of the baseline body weight at 2 consecutive visits. Percentages are based on the number of subjects who had the 7%/10% weight loss and had a value meeting the criteria noted in the row.

Programming Notes: Use the Table 14.4.1.5 shell for the following tables.

Table 14.4.1.5.1

Weight Summary (Lost/Gain \geq 7% or \geq 10%) during the Open-Label Study Period

Safety Population (Japan)

Table 14.4.1.6

Weight Summary (Lost/Gain \geq 7%, or \geq 10%) during the Open-Label Study Period by Concomitant Topiramate

Safety Population

Table 14.4.1.6.1

Weight Summary (Lost/Gain \geq 7%, or \geq 10%) during the Open-Label Study Period by Concomitant Topiramate

Safety Population (Japan)

Programming notes: Repeat Table 14.4.1.5 for 14.4.1.6 and 14.4.1.6.1 by subset by (a) subjects on concomitant topiramate, and (b) subjects not on concomitant topiramate.

Programming note: Use the Table 14.4.1.5 shell but only present for 5% to produce the following tables.

Table 14.4.1.7

Weight Summary (Lost/Gain \geq 5%) during the Open-Label Study Period

Safety Population

Table 14.4.1.7.1

Weight Summary (Lost/Gain \geq 5%) during the Open-Label Study Period

Safety Population (Japan)

Table 14.4.1.8

Weight Summary (Lost/Gain $\geq 5\%$) during the Open-Label Study Period by Concomitant Topiramate
Safety Population

Table 14.4.1.8.1

Weight Summary (Lost/Gain $\geq 5\%$) during the Open-Label Study Period by Concomitant Topiramate
Safety Population (Japan)

Table 14.4.4.1
 Tanner Staging by Age Group for Boys
 Safety Population

Age Group	Visit [1]	Tanner Stage	Gp1 (N = XX)	Gp2 (N = XX)	Gp3 (N = XX)	Gp4 (N = XX)	Gp5 (N = XX)	Gp9 (N = XX)
<7years	Baseline (OLE)(Day 1)	Stage I	XX (XX.X%)	XX (XX.X%)	XX (XX.X%)	XX (XX.X%)	XX (XX.X%)	XX (XX.X%)
		Stage II	XX (XX.X%)	XX (XX.X%)	XX (XX.X%)	XX (XX.X%)	XX (XX.X%)	XX (XX.X%)
		Stage III	XX (XX.X%)	XX (XX.X%)	XX (XX.X%)	XX (XX.X%)	XX (XX.X%)	XX (XX.X%)
		Stage IV	XX (XX.X%)	XX (XX.X%)	XX (XX.X%)	XX (XX.X%)	XX (XX.X%)	XX (XX.X%)

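### From Month 24 the analysis-window targets fall 5 days (10 at Month 36) after the scheduled visits, so the closest-to-target rule can prefer a later value to an on-schedule one

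*SAP*

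**What the plan says.** SAP Section 4, Tables 4 and 5, gives the study days of Visits 3 to 15 as "30, 60, 90, 180, 270, 365, 455, 545, 635, 725, 815, 905, 995". Visit 16 (Month 36) is on Day 1085 and Visit 17 on Day 1099.

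The window tables in Section 6.1.6 (7b to 7e), and the copy in the TLF shells for laboratory data and vital signs, use the same days as targets up to Month 21. After that the rows read "Month 24 (OLE) 680 to 774 730", "Month 27 (OLE) 775 to 864 820", "Month 30 (OLE) 865 to 954 910" and "Month 33 (OLE) 955 to 1044 1000" (window, then target). Month 36 has window 1045 to 1109 and target 1095.

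The selection rule is: "For multiple measurements within a time window, please use the closest to the target time point".

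Table 6 runs the Taper Period from the day after Visit 16 to Visit 17, and Section 6.1.5.1 ends the OLE phase at Visit 17. Table 7e assigns ECG and ECHO from the day after Visit 17 to Cardiac FU 1.

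For weight, the note to shell Tables 14.4.1.3 and 14.4.1.4 says "If a test is repeated at any given visit, the last non-missing result is used in the summary". The note to Table 14.4.1.5 says that with two or more assessments in an interval, "the assessment completed closest to the target time point are assessed".

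**The concern.** Section 6.1.6 intends the windows to sit around the target visit dates. From Month 24 they sit around different days, and no reason is given. Once the target lies after the visit, the rule no longer favours the scheduled assessment: it favours a somewhat later one.

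At Month 36 a later value is taken on a tapering dose or on no drug, and it could stand in the by-visit row in place of the end-of-treatment value. The primary objective is long-term safety, so the Month 24 to 36 rows are the ones a reader will turn to.

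The Month 36 window also runs past the end of the OLE phase, and for ECG and ECHO it overlaps Cardiac FU 1. Separately, the weight tables word the choice among repeats in two ways, which leaves room for different programming.

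**Working it through.** **Inputs.** Scheduled days s come from Tables 4 and 5. Targets t and windows come from Tables 7b to 7e and the shell.

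**Where the two sets come from.** The targets equal 365 × completed years + 30 × remaining months: Month 24 = 2 × 365 = 730, Month 27 = 730 + 90 = 820, Month 36 = 3 × 365 = 1095. From Month 12 the schedule equals 365 + 30 × (months − 12): Month 24 = 365 + 360 = 725, Month 36 = 365 + 720 = 1085. Both formulas reproduce the SAP's days exactly. The targets are reset at years 2 and 3 and the schedule is not.

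**Which later days win.** A value on day d > s displaces an on-schedule value when |d − t| < |s − t|, that is, when s < d < 2t − s.

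| Month | s | t | t − s | Winning days | Number | Tie |
|---|---|---|---|---|---|---|
| 1 to 21 | = t | = s | 0 | none | 0 | none |
| 24 | 725 | 730 | 5 | 726–734 | 9 | 735 |
| 27 | 815 | 820 | 5 | 816–824 | 9 | 825 |
| 30 | 905 | 910 | 5 | 906–914 | 9 | 915 |
| 33 | 995 | 1000 | 5 | 996–1004 | 9 | 1005 |
| 36 | 1085 | 1095 | 10 | 1086–1104 | 19 | 1105 |

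The rule does not resolve ties.

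**Month 36.** Of the 19 days, 14 (1086–1099) lie in the Taper Period. The dosing steps in Tables 2 and 3 cover at most 8 days (1086–1093), so 6 of the 14 (1094–1099) follow the last tapered dose. The other 5 (1100–1104) follow Visit 17. For an on-schedule subject, Days 1100–1109 fall both in the Month 36 window and in Cardiac FU 1 of Table 7e.

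**Sensitivity.** Section 3.3 gives the treatment period as 156 weeks, and 156 × 7 = 1092. If Visit 16 falls on Day 1092, the offset is 3 days and only Days 1093–1097 displace it.

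**Window limits.** The lower limits 775, 865 and 955 are the midpoints of adjacent current targets, for example (730 + 820)/2 = 775. The limit 1045 is 1000 + 45, and 1109 is 1095 + 14. If only the targets moved to 725 and 815, the midpoint would be 770. Days 771–774 would then stay in the Month 24 window although nearer to Month 27 (Day 771 is 46 days from 725 and 44 from 815). The same four-day error would arise at the next three boundaries.

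**After reconciliation.** With t = s in every row, no later day can displace an on-schedule value.

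**The case against.** **Replacement is not automatic.** This stands. A second value must exist: an unscheduled repeat or, at Months 24 to 33, an early-termination visit, which carries the same assessments. Tables 4 and 5 schedule no laboratory test, vital sign, ECG, ECHO or questionnaire at Visit 17, so at Month 36 only unscheduled values count. The contrast with Months 1 to 21 holds only for on-schedule visits; a visit made a few days early can lose to a later value there too.

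**Abnormal values are not lost.** A reader might infer that abnormal on-treatment results drop out of the safety report. The SAP does not support this. Section 6.4.9 lists all laboratory values and extreme results, the shells add listings of the most abnormal values, Section 6.4.5 lists out-of-range vital signs, and Table 14.4.1.5 has a block covering all OLE visits. Sections 6.4.6 and 6.4.7 leave ECG and ECHO to vendor reports. That repeats follow abnormal results is an assumption.

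**Taper data belong to the OLE phase.** Section 3.3.2 includes them in the safety analyses, and Table 6 would make Days 1100 onward post-OLE. That justifies keeping these data, but not letting them replace the Visit 16 value in the Month 36 row, since the Last Value row already takes values up to Visit 17.

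**The targets may be the intended days.** From Month 24 they equal the ends of the Table 7a seizure intervals. Day 1095 is also nearer than 1085 to 156 weeks (1092) and to 36 × 30.4 = 1094.4 days under Section 6.1.8. The document does not settle which set is right.

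**The weight notes need not conflict.** The last-non-missing rule can be read as a tie-break for repeats at one visit, and the closest-to-target rule as the choice within a window. A contradiction is not shown, but the wording leaves the choice open.

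**Conclusion.** The mismatch is real: 5 days at Months 24, 27, 30 and 33, and 10 days at Month 36, after exact agreement through Month 21. Under the stated rule a second value taken 1 to 9 days after an on-schedule Month 24 to 33 visit, or on Days 1086 to 1104, takes the place of the scheduled one. At Month 36 every such day is in or after the Taper Period.

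These ranges assume on-schedule visits and a day range applied as written, without the phase label overriding it. The effect is confined to descriptive by-visit summaries, and Section 6.1.2 plans no formal comparison between treatment groups. The number of subjects with a second value in these ranges is not given and is probably small. Severity: minor.

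**What to change.** - Reconcile the targets in Tables 7b to 7e and the shell copy with the visit days in Tables 4 and 5, and move the window limits with them. If the schedule is kept, the targets are 725, 815, 905, 995 and 1085, with windows 680–769, 770–859, 860–949, 950–1039 and Month 36 from 1040. If the targets are kept, the schedule rows must be brought into line instead.
- For the Month 36 row, use the Visit 16 value. Keep values after Visit 16 for Last Value, Cardiac FU and the listings. This also removes the overlap in Table 7e.
- In Tables 14.4.1.3 and 14.4.1.4, state that the Table 7c closest-to-target rule selects the assessment within the window, and that the last non-missing result applies only to repeats on the same day.

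If the schedule is kept, the cost is five targets and four window boundaries in each window table, one selection rule and one note. No new data are needed, and it can be done before the final analysis.

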6.4.10 Columbia-Suicide Severity Rating Scale

The Columbia–Suicide Severity Rating Scale (C-SSRS) is an assessment tool that evaluates suicidal ideation (including intent), and behavior. Baseline (core study) data were collected in the screening visit (Visit 1) of the Core study using the C-SSRS Children’s Baseline/Screening Assessment. For the current study, baseline (OLE) Treatment period data and Visits 3 through Visit 15 and EOS/ET (Visit 16) data are collected using the C-SSRS Children’s ‘Since Last Visit Assessment.

Subjects who are younger than 7 years chronologically, or who are judged by the investigator not to have the mental capacity to understand the questions as specified on the C-SSRS, will not complete the rating. The investigator should use his/her judgment to substitute intellectually appropriate questions to probe the tendency for self-harm.

If a subject with the intellectual capacity to complete the C-SSRS reaches 7 years of age during the study, use of the C-SSRS should be initiated at subsequent visits.

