6.4.10.1 Suicidal Ideation

[figure not shown]
The following outcomes are C-SSRS categories and have binary responses (yes/no):

Suicidal ideation is assessed as a “yes” answer at any time during the OLE treatment period to any one of the five questions (1-5) above. The number and percentage of subjects with suicidal ideation will be presented, as well as the number and percentage having a “yes” response to each category (1-5) at least once during the OLE period. The denominator will be the number of subjects completing the C-SSRS at least once during the OLE treatment period.

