No.of Subjects with Any Suicidal Ideation							
No.of Subjects with Any Suicidal Behavior							
No.of Subjects without Suicidal Ideation or Suicidal Behavior							
No. of Subjects with 'Self-injurious behavior without suicidal intent'							

C-SSRS: Columbia Suicide Severity-Rating Scale

[1] Counts are based on response at Visit 1 of the OLE Period.

[2] Counts are based on responses during the OLE period.

Note: each subject is counted only once, using the most severe C-SSRS response category during treatment. No event=0; suicidal ideation=1, 2, 3, 4, 5; suicidal behavior=6, 7, 8, 9, 10. See SAP Section 6.4.10.

N=number of subjects with baseline AND post-baseline C-SSRS assessment. Cell frequencies are to be divided by the total N in the relevant treatment group and multiplied by 100 to get the cell %.

Programming note: Use the Table 14.4.5.1 shell for:

Table 14.4.5.1.1
Number of Subjects with Suicidal Ideation, Suicidal Behavior and Self Injurious Behavior Without Suicidal Intent
Based on the (C-SSRS) during Treatment
Safety Population (Japan)

Table 14.4.5.2
 Number of Subjects with Suicide-Related Treatment-Emergent Events Based on the (C-SSRS) during Treatment
 Safety Population

BASELINE (OLE)	----Most Severe Post Baseline Potentially Suicide-Related Category----			
	No suicidal ideation or behavior	Suicidal ideation	Suicidal behavior	Total
Gp1 (N=xxx)				
No suicidal ideation or behavior	XX (XX.X%)	XX (XX.X%)	XX (XX.X%)	XX (XX.X%)
Suicidal ideation	XX (XX.X%)	XX (XX.X%)	XX (XX.X%)	XX (XX.X%)
Suicidal behavior	XX (XX.X%)	XX (XX.X%)	XX (XX.X%)	XX (XX.X%)
Gp2 (N=xxx)				
No suicidal ideation or behavior	XX (XX.X%)	XX (XX.X%)	XX (XX.X%)	XX (XX.X%)
Suicidal ideation	XX (XX.X%)	XX (XX.X%)	XX (XX.X%)	XX (XX.X%)
Suicidal behavior	XX (XX.X%)	XX (XX.X%)	XX (XX.X%)	XX (XX.X%)
Gp3 (N=xxx)				
No suicidal ideation or behavior	XX (XX.X%)	XX (XX.X%)	XX (XX.X%)	XX (XX.X%)
Suicidal ideation	XX (XX.X%)	XX (XX.X%)	XX (XX.X%)	XX (XX.X%)
Suicidal behavior	XX (XX.X%)	XX (XX.X%)	XX (XX.X%)	XX (XX.X%)
Gp4 (N=xxx)				
No suicidal ideation or behavior	XX (XX.X%)	XX (XX.X%)	XX (XX.X%)	XX (XX.X%)
Suicidal ideation	XX (XX.X%)	XX (XX.X%)	XX (XX.X%)	XX (XX.X%)
Suicidal behavior	XX (XX.X%)	XX (XX.X%)	XX (XX.X%)	XX (XX.X%)
Gp5 (N=xxx)				
No suicidal ideation or behavior	XX (XX.X%)	XX (XX.X%)	XX (XX.X%)	XX (XX.X%)
Suicidal ideation	XX (XX.X%)	XX (XX.X%)	XX (XX.X%)	XX (XX.X%)

Suicidal behavior	XX (XX.X%)	XX (XX.X%)	XX (XX.X%)	XX (XX.X%)
Gp9 (N=xxx)				

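### The note under the Table 14.4.5.1 shell contradicts SAP 6.4.10.1 and 6.4.10.2 on who counts as having suicidal ideation and on the denominator

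*SAP*

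**What the plan says.** **SAP body.** Section 6.4.10.1 treats a subject as having suicidal ideation after a yes "answer at any time during the OLE treatment period to any one of the five questions (1-5) above". Section 6.4.10.2 does the same for behavior with questions 6 to 10. Section 6.4.10.3 adds a composite over questions 1 to 10, and 6.4.10.4 counts self-injury without suicidal intent from question 11. On the divisor, 6.4.10.1 says: "The denominator will be the number of subjects completing the C-SSRS at least once during the OLE treatment period". Section 6.4.10.2 repeats this.

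Section 6.4.10 exempts children under 7 and those judged unable to understand the questions. It adds that if a child with the capacity to complete the scale "reaches 7 years of age during the study, use of the C-SSRS should be initiated at subsequent visits".

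**Shell.** Table 14.4.5.1 has a Baseline block (OLE Visit 1) and an OLE Period block. Each block has a row labelled "No.of Subjects with Any Suicidal Ideation" and separate rows for behavior, for neither, and for self-injury. The note beneath says that "each subject is counted only once, using the most severe C-SSRS response category during treatment", with this coding: "No event=0; suicidal ideation=1, 2, 3, 4, 5; suicidal behavior=6, 7, 8, 9, 10". It then sets "N=number of subjects with baseline AND post-baseline C-SSRS assessment" and continues: "Cell frequencies are to be divided by the total N in the relevant treatment group and multiplied by 100 to get the cell" percentage. The note refers the programmer to SAP Section 6.4.10. The same shell is reused for the Japan version, Table 14.4.5.1.1.

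**The concern.** A row that claims to show any ideation cannot be filled by a rule that places each subject in a single worst category. Nor can one percentage be taken over both divisors, because the groups differ by design: 6.4.10 deliberately starts the scale mid-study for some children, who then have OLE ratings but no baseline.

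Long-term safety is the primary objective. Table 14.4.5.1 is listed for the interim analysis and the 120-day safety update, and its Japan copy for the 2020 Japan report. A programmer who follows the footnote and one who follows 6.4.10 would produce different tables, and the SAP does not say which governs. With rare events, one or two misplaced subjects matter to the reader of such a table.

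**Working it through.** The SAP states no C-SSRS count or rate, so there is no figure to reproduce. The check sets the two rules side by side.

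| | SAP 6.4.10.1 and 6.4.10.2 | Table 14.4.5.1 note |
|---|---|---|
| Ideation | any yes to questions 1–5 in the OLE | worst category falls in 1–5 |
| Behavior | any yes to questions 6–10 in the OLE | worst category falls in 6–10 |
| Can one subject be in both? | yes | no |
| Divisor | rated at least once in the OLE | rated at baseline and after it |

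**Step 1, the count.** Let *A* be the subjects with any ideation in the OLE and *B* those among them who also report behavior. Section 6.4.10.1 reports *A*. Every behavior code exceeds every ideation code, so under the note those *B* subjects appear only in the behavior row, and the ideation row shows *A* − *B*. The shortfall is exactly *B*. The behavior row is not affected by the ranking.

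**Step 2, the divisor.** Take an OLE rating to mean one after Visit 1. Let *D* be the subjects with at least one such rating and *M* those among them without a Visit 1 rating. Section 6.4.10.1 divides by *D*; the note divides by *D* − *M*. The OLE lasts 36 months, so a child aged at least 7 − 3 = 4 and under 7 at Visit 1 can reach 7 during it. If that child has the capacity to complete the scale, the child is in *D* and in *M*.

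**Step 3, the percentage.** If events in the *M* subjects stay in the numerator, the shell gives (*A* − *B*)/(*D* − *M*) against *A*/*D*. The shell percentage is the higher one when *B*/*A* < *M*/*D*, and the lower one when *B*/*A* > *M*/*D*. If those events are dropped, the numerator falls further.

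**Illustration on assumed counts, none from the SAP.** Take *D* = 100, *M* = 10 and *A* = 6, with all 6 rated at Visit 1 unless stated.

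- Section 6.4.10.1: 6/100 = 6.0%.
- Shell, *B* = 0: 6/90 = 6.7%.
- Shell, *B* = 2: 4/90 = 4.4%.
- Shell, *B* = 6: 0/90 = 0%.
- Shell, *B* = 2, with one of the 4 ideation-only subjects lacking a Visit 1 rating: 3/90 = 3.3% if that event is dropped, 4/90 = 4.4% if it is kept.

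The direction depends on overlap and on missing baselines, and the SAP gives neither.

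**Step 4, does anything reconcile the rules?** The OLE block's footnote says only that counts come from responses in that period. It neither restores overlapping counts nor changes N. The note's coding stops at 10, so it does not say how the once-only rule applies to question 11.

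**The case against.** The strongest defence is that the note is unclear rather than wrong. The row label says any, the note points to 6.4.10, and the rule cannot be fully once-only because self-injury lies outside its coding. The OLE block also begins with a row for the number of subjects completing the scale, with no baseline condition, so a reader could rebuild the 6.4.10.1 percentage. No suicidality case vanishes on account of the ranking: a subject with both moves to the more severe row, the ideation and behavior rows still sum to the composite of 6.4.10.3, and Listing 16.2.9.2 shows the individual ratings.

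Much of this stands as mitigation, but it does not remove the conflict. The note states its ranking and its N outright, and its explicit instruction is to divide by that N. The row of completers allows a different divisor but cannot recover an ideation count from which overlapping subjects have been removed.

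Three stronger readings are tempting, and the documents do not support them:

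- **Children who turn 7 on study lose their events from the table.** They are outside N, but the note does not say that events outside N are discarded.
- **Ideation is certainly undercounted by some fraction.** Under the ranking rule the shortfall equals the overlap, which may be zero. The capacity condition in 6.4.10 may also leave few children who start the scale mid-study.
- **The reporting of suicidality as an adverse event of special interest is compromised.** Tables 14.3.1.7 and 14.3.1.8 summarise adverse events, not C-SSRS responses, and this note does not touch them.

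**Conclusion.** Wrong as written; minor to moderate, in a descriptive safety table with no inference attached. Two contradictions are certain from the text. The note makes ideation and behavior mutually exclusive where 6.4.10.1 and 6.4.10.2 do not, and it requires a baseline rating where they do not.

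Under the ranking rule alone, the ideation count can match or fall below the 6.4.10.1 count but cannot exceed it. The percentage may be higher or lower. No size can be given without the number of subjects with both outcomes, the number rated in the OLE without a Visit 1 rating, and a statement on whether events outside N are kept. The conclusion assumes that the programmer follows the footnote as it stands.

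**What to change.** Amend the note under Table 14.4.5.1, and so Table 14.4.5.1.1:

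1. Count the ideation, behavior and self-injury rows independently, each on any yes in the period, as in 6.4.10.1, 6.4.10.2 and 6.4.10.4. Delete the once-only rule from this table.
2. In the OLE Period block, divide by the subjects with at least one OLE rating, which is the block's own row of completers. In the Baseline block, divide by the subjects rated at Visit 1.
3. Because the ideation and behavior rows may then overlap, obtain the composite of 6.4.10.3 as completers minus the row for neither, or add a row for it.

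Keep the most-severe category and the baseline-plus-post-baseline requirement for the shift tables, 14.4.5.2 and 14.4.5.2.1, where a subject needs both ratings and exactly one cell.

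The cost is a footnote edit and a small programming change. No new data are needed.
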